Study Duration:	November 1, 2021 to April 30, 2024
Participant Duration:	4 to 6 weeks

Primary Objective:	To determine the feasibility, acceptability, and potential efficacy of the culturally competent communication to improve engagement in ACP (i.e., end-of-life discussions with providers and families, completion of advance directives) for Latino patients with advanced cancer.
Secondary Objectives:	Not applicable
Exploratory Objectives:	Not applicable
Endpoints:	
Feasibility will be measured by intervention completion (Benchmark: $\geq 70\%$ complete the intervention sessions).
 
Acceptability will be measured by a single-item question assessing helpfulness of the intervention (1 = not at all helpful, 5 = very helpful) as well an open-ended question about helpfulness of the intervention ("What was helpful about the intervention?") (Benchmark: $\geq 70\%$ rate it as "helpful" or "very helpful").
 
Advance Care Planning Readiness will be measured using the Advance Care Planning Engagement Survey, which is a validated 49-item scale ($\alpha=.94$)¹ designed to assess knowledge, readiness/motivation, and self-efficacy of ACP. Engagement in ACP will measure two key elements of ACP. First, EOL care discussions will be measured by asking patients to self-report whether they have discussed any of the following: (1) wishes they have about the care they would like to receive if they were dying and/or (2) advance care directives, with an oncology provider or family member: DNR orders, living wills, durable powers of attorney for health care, assignments of health care proxies (yes/no format). Second, completion of advance directives will be assessed by examining the medical chart for completed advance directive documents (DNR order, living will, durable power of attorney, health care proxy).

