5.1 Schedule of Assessments

Table 1. Schedule of trial events

	Baseline	Post-intervention (with 1 week of completing intervention)	3 mos. after completion of intervention	Off Study
Informed consent	X			
Demographics	X			
Clinical variables				X
Acceptability		X		
Usability		X		
Feasibility		X		
Quality of life	X	X		
Cultural beliefs (Fatalismo, personalismo, respeto)	X	X		
Familial beliefs (Familismo, filial duty)	X	X		
Religious/spiritual beliefs (Religious coping, religious beliefs about end-of-life medical care)	X	X		
Terminal illness acceptance	X	X		
Illness understanding	X	X		
Readiness for ACP	X	X		
Engagement in ACP	X	X		
Healthcare utilization	X	X	X	
Goal-concordant care	X	X	X	

6. Data Reporting / Regulatory Considerations

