as well as satisfaction and helpfulness ratings to determine feasibility and acceptability based on those values being equal to or greater than 70%. We will also conduct qualitative analyses on the open-ended questions related to helpfulness. Thematic analysis using an iterative process will be conducted for all qualitative analyses.⁵⁵⁻⁵⁹ A coding scheme and codebook will be created to analyze transcripts of the responses to the open-ended question. Transcripts will be coded separately by two individual coders for manifest (e.g., frequencies) and latent (e.g., underlying themes) variables. If discrepancies occur, a third coder will resolve these conflicts. Interviews will continue until thematic saturation is achieved.^{60,61} Based on our prior field testing of interventions with patients with advanced illness, we anticipate reaching saturation with n=10 participants. Thus, n=25 in the experimental condition should be well powered to reach thematic saturation.

To examine potential efficacy, preliminary analyses will utilize t-tests to compare the two groups on baseline characteristics (e.g., education, age). Using a criterion of $p < .10$, any variables that are different among the groups will be included in the final logistic regression models as potential confounders. To test the study aim, five separate logistic regression models will be run in which ACP outcomes (yes/no to EOL discussions with family and providers; and the completion of advance directives DNR, health care proxy, and living will) will be predicted by the group variable (CCC intervention vs. control). The statistical power of the proposed logistic regressions to detect a minimum odds ratio of 2.0 for dichotomous outcome measures of ACP, for a two-tailed test with power $(1 - \beta)$ equal to 0.80, and $\alpha = 0.05$, requires a sample size of 113. Our proposed sample size of n=50 will be underpowered if the effect size is small but adequately powered if it is large. However, this study is a preliminary pilot and the main focus and goal of this is to determine feasibility, acceptability, and to provide preliminary data to inform a fully-powered RCT in future research (R01 submission).

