7.1 Randomization. We will utilize stratified randomization at the level of each site to ensure balance across the interventional and control groups at the level of each site. To randomize, we will employ a random number generator to randomize participants to study arms at the level of each site. To ensure randomization was effective, separately for each binary outcome, we will perform a two-sample proportions test to test if the rate of outcomes is significantly different between intervention and control groups. Separately for each continuous outcome, we will perform a two-sample unpaired t-test or unpaired Wilcoxon test (as appropriate) to test if the rate of outcomes is significantly different between intervention and control groups.

7.2 Missing data. To reduce missing data, study staff will conduct interviews rather than relying on written self-reports. This approach has been used previously in our prior work to help reduce data that is missing due to patients accidentally overlooking or missing items or requiring clarification of certain terms (e.g., what is an advance directive). Due notice is taken to ensure that patients know that they are free to skip items they prefer not to answer.

8. Adverse Event Reporting Requirements

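### No efficacy analysis is specified for the ACP Engagement Survey endpoint; the only between-arm test that could cover it is unadjusted and labelled a randomization check

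*Combined protocol and SAP*

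**What the plan says.** The Endpoints row of the Protocol Summary lists ACP readiness, which "will be measured using the Advance Care Planning Engagement Survey, which is a validated 49-item scale". Section 3.6 B describes the same instrument. In Table 1 (Section 5.1) the row "Readiness for ACP" is marked at baseline and post-intervention, and Section 3.8 gives control patients both assessments.

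The objective (Protocol Summary and 1.1.1) is to "improve engagement in ACP (i.e., end-of-life discussions with providers and families, completion of advance directives". The survey is not named there. Section 7 states the efficacy analysis: "To test the study aim, five separate logistic regression models will be run in which ACP outcomes" are predicted by group. The outcomes are "yes/no to EOL discussions with family and providers; and the completion of advance directives DNR, health care proxy, and living will". The Analytic Plan in the Protocol Summary lists the same five.

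Covariate adjustment is tied to those models: "any variables that are different among the groups will be included in the final logistic regression models as potential confounders", with p < .10 as the criterion.

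Section 7.1 then adds a set of tests. It opens with "To ensure randomization was effective, separately for each binary outcome, we will perform a two-sample proportions test" and continues with "Separately for each continuous outcome, we will perform a two-sample unpaired t-test or unpaired Wilcoxon test (as appropriate". It names neither the survey nor a time point.

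**The concern.** There are two defects. First, a listed endpoint with a baseline measurement has no designated efficacy analysis, and no model in the plan uses its baseline score to sharpen the comparison of its post-intervention score. Second, the only sentence that could supply a comparison gives it the wrong purpose. Post-intervention differences are what the intervention is meant to produce, so they cannot show whether allocation was sound.

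At stake is what the pilot passes on. Section 7 says it should provide preliminary data for a fully powered trial. An adjusted difference with its interval, the SD and the baseline-to-post correlation of the survey are useful planning inputs, and the plan asks for none of them. The survey also sits close to what PLAN teaches: Section 3.7 starts from knowledge, motivation and self-efficacy, which are the domains the survey is said to assess.

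**Working it through.** **Step 1: coverage of the survey.**

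| Place in the plan | Covers the survey? | Uses its baseline score? |
|---|---|---|
| Protocol Summary, Endpoints | Yes, as an endpoint | n/a |
| Table 1 | Yes, baseline and post | n/a |
| Section 7, five logistic models | No, all yes/no outcomes | At most as a covariate for another outcome, if the arms differ at p < .10 |
| 7.1, continuous outcomes | Only generically | No |

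Section 7.1 can be read in two ways. If it means post-intervention scores, the survey gets an unadjusted test with a stated purpose the test cannot serve. If it means baseline scores, the survey gets no between-arm outcome test. Under both readings the efficacy analysis is missing.

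**Step 2: what baseline adjustment would add.** The plan has no power figure for the survey. Its sample size of 113 concerns yes/no outcomes at an odds ratio of 2.0 and is not an input here.

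Inputs from the plan: 25 per arm, two-sided alpha 0.05.

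Assumed, because the plan gives neither: a true effect d of 0.5 or 0.65 SD, and a correlation r of 0.3, 0.5 or 0.7. Site is assumed to explain no further variance.

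Formulas:
- The residual SD under ANCOVA is s = √(1 − r²) in units of the outcome SD. This gives 0.954, 0.866 and 0.714 for r = 0.3, 0.5 and 0.7; unadjusted, s = 1.
- The noncentrality parameter is (d/s) × √(25/2) = (d/s) × 3.536.
- Power comes from the noncentral t distribution. It has 48 df unadjusted and 45 df for ANCOVA (one df for baseline score, two for three sites).

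Worked example at d = 0.5: unadjusted, 0.5 × 3.536 = 1.768, power 41%. At r = 0.7, (0.5/0.714) × 3.536 = 2.475, power 68%.

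| Effect | Unadjusted | r = 0.3 | r = 0.5 | r = 0.7 |
|---|---|---|---|---|
| 0.5 SD | 41% | 44% | 52% | 68% |
| 0.65 SD | 61.5% | 65% | 74% | 88% |

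**Step 3: precision, which matters more in a pilot.** The expected 95% CI half-width is t × s × √(2/25), with √(2/25) = 0.283. Unadjusted it is 2.011 × 1 × 0.283 = 0.57 SD. With ANCOVA (t = 2.014) it is 0.54, 0.49 and 0.41 SD at r = 0.3, 0.5 and 0.7. The residual variance falls by r², that is by 9%, 25% and 49%.

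**The case against.** The strongest reply is that the analysis follows the objective. The plan defines engagement as discussions and directives, the five models test exactly those, secondary and exploratory objectives are marked not applicable, and the survey measures readiness rather than behaviour. This stands as a reason not to make the survey the main efficacy outcome. It does not excuse leaving a listed endpoint without an analysis.

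A second reply is that this is a pilot and already concedes limited power. That is fair as to emphasis: the case for ANCOVA rests on a better estimate, not on reaching 80%. But Section 7 declines inferential statistics only for feasibility and acceptability, and it plans efficacy tests.

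A third reply is that the gain may be small. That also stands: at r = 0.3 power rises by only about 3 to 4 points. Attrition would lower every figure. With an assumed 20 analysed per arm and 0.65 SD, power is 52% unadjusted and 55% to 80% with ANCOVA over r = 0.3 to 0.7.

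A reader might also infer more than the documents support:
- *That the trial throws away its most precise efficacy measure.* The score is collected and may be compared under 7.1. Ranking its precision against the yes/no outcomes needs similar standardized effects on both, and the plan gives no basis for that.
- *That the binary outcomes are all rare.* The background figures for Latinos are 32% for end-of-life discussions, 9% for a living will and 4% for a proxy. The first is not rare, and none is stated as an expected control rate.
- *That a real survey effect would be declared failed randomization.* Section 7.1 attaches no consequence to a significant result and may mean baseline values.

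**Conclusion.** The point holds as a gap in the analysis plan with a better method available from data already being collected. The survey is a listed endpoint measured before and after, it is in none of the efficacy models, and 7.1 offers at most an unadjusted test under a purpose that a comparison of post-intervention outcomes cannot serve. This conclusion rests on the text alone and does not depend on any assumed effect.

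The size of the gain does depend on assumptions. Over r = 0.3 to 0.7, ANCOVA adds about 3 to 27 percentage points of power at 0.5 SD and about 4 to 27 at 0.65 SD, and narrows the expected interval from 0.57 SD to between 0.54 and 0.41 SD either side. The gain is small at low correlation and substantial at high correlation, and the documents cannot say which applies. The change should be made, but it does not threaten the feasibility and acceptability aims.

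**What to change.** In Section 7 and the Analytic Plan of the Protocol Summary, add one pre-specified model: an ANCOVA of the post-intervention survey score on arm, adjusted for baseline score and site, since site is the randomization stratum. Report the adjusted mean difference with its 95% CI. State that it supports the binary engagement outcomes that define the objective. Report the SD and the baseline-to-post correlation as planning inputs for the future trial.

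In 7.1, remove the outcome tests as a check on randomization. If a view of baseline balance is wanted, say that baseline values are meant and present them descriptively by arm.

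The cost is one more model and revised wording. No new data, visits or patients are needed.

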8.1 Potential Adverse Events

Potential adverse events (AEs) for this project are all non-medical in nature. Participants may experience mild distress when discussing the status of the patients' cancer, decision-making, or care. Study staff may become aware of adverse events through participant self-report, routine study assessments, or study staff interactions with participants.

We will use standard NIH definitions of AEs/SAEs and UPs as follows:

Adverse Event (AE): Any untoward or unfavorable medical occurrence in a human study participant, including any abnormal sign (e.g. abnormal physical exam or laboratory finding), symptom, or disease, temporally associated with the participants' involvement in the research, whether or not considered related to participation in the research. The most likely event for the present study is elevated psychological distress.

Serious Adverse Event (SAE): Any adverse event that: Results in death; Is life threatening, or places the participant at immediate risk of death from the event as it occurred; Requires or prolongs hospitalization; causes persistent or significant disability or incapacity; Results in congenital anomalies or birth defects; Is another condition which investigators judge to represent significant hazards. An example in the present study is a hospitalization or institutionalization or suicidal ideation.

Unanticipated Problem (UP): Any incident, experience, or outcome that is: Unexpected, in terms of nature, severity, or frequency; related or possibly related to participation in the research; and suggests that the research places participants or others at a greater risk of harm (including physical, psychological, economic, or social harm) than was previously known or recognized.

We will use the following grading and relatedness scales in use at FHCC, UT Southwestern, and Confluence Health for severity rating and relatedness rating:

Grading scale:

0. No adverse event
1. Mild AE – No treatment needed
2. Moderate AE – Resolved with treatment
3. Severe AE – Inability to carry on normal activities, required professional medical attention
4. Life-threatening or disabling AE
5. Fatal AE

Relatedness scale:

- Definitely related
- Probably related
- Possibly related
- Unlikely to be related
- Definitely not related

To summarize, potential adverse events (AEs) for this project are all non-medical in nature and are expected to be graded as mild to moderate. Participants may experience mild distress when discussing the status of the patients' prognosis or advance care planning. Serious adverse events (SAE) will include the following: suicidal ideation and/or discussing plans to harm another individual. Study staff may become aware of adverse events through participant self-report, routine study assessments, or study staff interactions with participants.

An unanticipated problem (UP) in the present study would include physical harm of any form to patients, as the proposed study only poses to potentially increase distress. As outlined in NIH policy, the AEs are expected to be mild to moderate in severity; the SAEs are expected to be serious in severity; and the UPs are expected to be mild to moderate in severity.

Based on our prior work, we anticipate that AEs will occur rarely (in less than 2% of cases based on prior studies); SAEs to be 0% (based on prior work); and UPs to be less than 1% based on prior work. In most cases, only an AE of distress is expected to be directly related to study procedures whereas SAEs and UPs are rarely linked to study procedures directly in similar work.

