3.8 Interviewer Training and Instrument Administration

Interviewer Training. Staff working on this protocol have extensive experience interviewing

patients with advanced cancer in an end-of-life care settings from our previous NCI-funded studies. These fully trained, experienced interviewers will train new interviewers. Training will consist of learning the interview question prompts/guides, practice sessions, and instruction in administration of surveys, including IRB approved procedures for approaching potential study participants. Newly trained interviewers will be required to have a high degree of inter-rater-reliability (e.g., $\kappa=0.85$) with fully-trained, experienced interviewers on core assessments (e.g., religious beliefs about end-of-life medical care) before they will be allowed to collect data for the study.

Scheduling of Assessments. Study staff will contact enrolled patient study participants to schedule their interviews. Patients will be given the option to communicate about their assessments and the scheduling of the assessments via phone calls, emails, and/or text messages. Patient assessments will be scheduled to occur at the earliest convenient time for the participant following study enrollment. All baseline assessments will be given first. Then, patients will engage in their first intervention session within one week of completing a baseline assessment. The three intervention sessions will then be given approximately a week apart, taking approximately four weeks to complete. After completion of the intervention, patients will complete a post-intervention assessment within one week. Finally, a brief three month follow up will occur that extracts data from their EHR on healthcare utilization. For those in the control condition, they will receive a baseline assessment and then a “post-intervention” session four weeks later, which is the expected span of time between baseline and post-intervention assessments for those in the experimental condition. Three month follow up data extraction will occur for subjects in experimental and control conditions.

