3.9 Intervention Administration

A total of 50 Latino advanced cancer patients will be enrolled in this study and randomly assigned to the intervention (n=25) or control (n=25) condition. Pre-intervention, patients'

communication goals will be assessed. Then, patient will participate in the intervention or a usual care control condition. After participating in the intervention or control condition, patients' engagement in ACP will be assessed to determine if the intervention improved ACP engagement and planning.

The intervention itself will be administered by a fully trained, licensed social worker via telephone. This interventionist will use a culturally competent communication intervention to "coach" patients in how to be motivated for and to actually engage in ACP, and will be bilingual in Spanish and English.

Patients randomized into the control group will receive usual care. For usual care, patients will engage in standard care with no modifications. Thus, ACP discussions will only occur as they do in usual clinical care (i.e. brought up in clinical encounters).

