8.2 AE/SAE Reporting

To identify possible AEs and SAEs, all study staff will be trained in identifying possible AEs or SAEs and will be required to keep a written log after each participant completes study procedures. In the event an AE or SAE is noticed, study staff will notify the PI either within 24 hours (for SAEs) or within five days (for AEs). Additionally, the PI will review all study materials, including recording interviews and answers to study questions to ensure that no AEs or SAEs go undetected.

All SAEs noted by study staff will be discussed with the PI or designee and reported within 24 hours of discovery by study staff to the IRB and the NCI Program Officer. The PI is required to report adverse events to the Institutional Review Board (IRB) on an ongoing basis. In addition, yearly IRB renewal submissions require detailed adverse event reporting, which will also be sent to the NCI Program Officer and the grant PI ([name]). Adverse events are also reported as part of the progress reports in the non-competitive and competitive renewals for the NIH. All study staff will complete the NIH required training in participation and conduct of studies that involve human subjects. If study staff discover any untreated physical conditions, they will refer participants to appropriate treatment immediately.

Some participants will be receiving active treatment at the time of study participation; therefore, fluctuations in cancer-related symptoms will not be considered adverse events related to the study. The PI will discuss safety concerns, adverse events, participant complaints and, if any, protocol violations with co-investigators as well.

Meetings with co-investigators will be used to determine if any additional procedures are needed to augment data and safety monitoring. When SAEs occur that are unanticipated, they will be reported to and verified by [name], and reported to the IRB and the NCI Program Officer.

After reporting to the IRB, the PI will determine necessity for further reporting and next steps, which will include the following:

- No further reporting of a “definitely not related” AE (but not SAE) will occur.
- All deaths will be reported to the IRB and NCI Program Officer within 24 hours of learning about this event.

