In addition, participants may find engagement in the intervention to be upsetting, particularly due to the potential for family conflict to arise. In addition, discussing advance care planning and end-of-life goals of care can be difficult. Patients will be in weekly contact with study interventionists who will be licensed social workers with experience working with medically ill patients and their families. These social workers will have the skills to assess exacerbations in distress in study participants and provide appropriate support. Additionally, the social workers will provide patients with continued support throughout the intervention. In the event a study participant requires a higher level of care than provided in this study, a FHCC licensed on call psychiatrist or mental health professional, UT Southwestern Licensed Clinical Psychologist, or a Confluence Health licensed on call psychiatrist or mental health professional will be consulted and the participant will be referred to the appropriate level of care. [name] (PI) will also be contacted if a patient endorses suicidal ideation. If additional intervention is necessary, [name] will coordinate with FHCC's clinical team for referral and care, [name] will coordinate with UT Southwestern's Psychiatry Department, and [name] will coordinate with a mental health professional at Confluence Health. Study participants

who express a desire following the post-intervention interview to talk at greater length about issues raised during the study will be encouraged to call study staff at the telephone number provided, and should they want a referral for psychological counseling, study staff will provide them with a referral to a mental health professional at a location that is convenient for them.

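### Adverse-event ascertainment is largely passive and tied to study contact, with four scheduled post-baseline contacts in PLAN against one in control, so by-arm counts of contact-detected events, chiefly distress, are expected to be biased upward in PLAN

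*Combined protocol and SAP*

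**What the plan says.** Section 8.1 gives three routes by which AEs come to light: "Study staff may become aware of adverse events through participant self-report, routine study assessments, or study staff interactions with participants". Section 8.2 adds that staff are "required to keep a written log after each participant completes study procedures", and that the PI reviews study materials and answers so that events are not missed. The schedule of assessments (Section 5.1) has no row for AEs. No standard AE question or look-back period is given elsewhere.

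Study contact differs by arm. For PLAN, Section 3.8 says "The three intervention sessions will then be given approximately a week apart, taking approximately four weeks to complete" and then "After completion of the intervention, patients will complete a post-intervention assessment within one week". For controls it says "For those in the control condition, they will receive a baseline assessment and then a" nominal post-intervention "session four weeks later, which is the expected span of time between baseline and post-intervention assessments for those in the experimental condition". Section 3.9 confirms: "Patients randomized into the control group will receive usual care". Section 9.1 states that "Patients will be in weekly contact with study interventionists who will be licensed social workers", and credits them with the skill to recognise worsening distress. Section 9.2.3 promises close monitoring of those receiving the intervention. Controls have no interventionist.

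Some sources cover both arms: the post-intervention assessment, including FACT-G; chart review during the study; and extraction of healthcare utilization from the EHR to three months (Sections 3.8 and 5.1). None of the chart or EHR review is named as an AE source, although Section 8.2 makes hospitalization, emergency visit and death reportable triggers.

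**The concern.** Psychological distress is the event that Section 8.1 considers most likely, and Section 9.2.3 adds family conflict. A chart is unlikely to show either in mild form; they come to light mainly when someone talks with the patient. PLAN patients have more such conversations, most of them with a clinician skilled in recognising distress.

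Section 6.2.4 commits the study to AE reporting at its conclusion, and Section 7 says the pilot is to inform a fully powered trial. If AEs are tabulated by arm, an excess in PLAN could be read as harm when it reflects closer observation, or a real excess could be dismissed as closer observation. A low control count resting on one unstructured contact would say little about the background rate. This cannot be repaired once the data are in.

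**Working it through.** The plan gives no by-arm AE figure or AE power statement, so there is nothing to reproduce.

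**Contacts after baseline (Section 3.8).** PLAN: 3 sessions + 1 assessment = 4. Control: 1 assessment. Reminder calls or texts (Section 3.5) are not counted because their number is not stated.

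**Timing (Section 3.8).** PLAN: up to 1 week to the first session + about 4 weeks of sessions + up to 1 week to the assessment = up to about 6 weeks from baseline. Control: 4 weeks.

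**Detection with equal true harm.** Let d be the probability that an existing AE is picked up at one contact. The documents do not give d; it is an assumption. Contacts are taken as independent and equally sensitive, and an AE is taken to stay detectable until the last contact.

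- Control: d.
- PLAN, onset before the first session: 1 − (1 − d)^4.
- PLAN, onset spread evenly over the four intervals, so that 1, 2, 3 or 4 contacts follow: the mean of 1 − (1 − d)^k over k = 1 to 4.

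| d | Control | PLAN, early onset | Ratio | PLAN, even onset | Ratio |
|---|---|---|---|---|---|
| 0.2 | 0.200 | 0.590 | 3.0 | 0.410 | 2.0 |
| 0.3 | 0.300 | 0.760 | 2.5 | 0.557 | 1.9 |
| 0.5 | 0.500 | 0.938 | 1.9 | 0.766 | 1.5 |

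For example, at d = 0.2 with even onset: (0.200 + 0.360 + 0.488 + 0.590)/4 = 0.410, and 0.410/0.2 = 2.0. Over a wider range the ratios are 3.44 (early) and 2.26 (even) at d = 0.1, and 1.11 and 1.08 at d = 0.9. The direction is the same throughout; the size depends on d and on onset.

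**Observed counts.** Section 8.1 anticipates AEs in fewer than 2% of cases. Take 2%, 25 per arm, d = 0.3 and early onset, with each arm's count binomial:

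- Expected PLAN: 25 × 0.02 × 0.760 = 0.38.
- Expected control: 25 × 0.02 × 0.300 = 0.15.
- Both zero: (1 − 0.0152)^25 × (1 − 0.0060)^25 = 0.59. Equal counts: 0.62. PLAN higher: 0.28.

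At an assumed AE rate of 20%, with d = 0.3 and early onset, expected counts are 25 × 0.20 × 0.760 = 3.80 and 25 × 0.20 × 0.300 = 1.50, and PLAN is higher with probability 0.80.

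**With the same enquiry in both arms**, detection is equal for any d and the ratio is 1.00.

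**The case against.** Several stronger readings are tempting, and the documents do not support them.

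- **That AEs are found only through chance contact.** Patients may self-report, the post-intervention assessment is scheduled in both arms, and the PI's review reaches both arms' answers. This stands. The log and the PI's review do, however, draw on material that PLAN generates in larger quantity.
- **That the by-arm counts will differ.** The bias is in the expected counts. At the anticipated rate, equal counts, mostly 0 against 0, are the likeliest result. This stands too. That rate comes from prior studies, though, and Section 8.2 itself says hospitalizations and other illness-related events may occur in this population and will be reported, so total counts need not stay near zero.
- **That hospital and emergency visits will be found more often in PLAN.** They may be noticed sooner, but chart and EHR review covers both arms. The gap is only that this review is not linked to AE capture.
- **That any PLAN excess is an artefact.** Section 8.1 expects distress when difficult subjects are discussed, and only PLAN has coaching sessions. Some excess could be a real effect of the intervention.

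It is also fair to say that Section 7 plans no by-arm AE comparison, that Section 6.2.4 does not say AE reporting will be by arm, and that closer monitoring of coached patients serves their protection. These points limit the consequence but leave the unequal ascertainment in place, and a two-arm trial's AE results are likely to be compared by arm.

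**Conclusion.** The point holds in a limited form. Followed as written, the plan yields counts of contact-detected AEs, chiefly distress, that are not comparable between arms and are expected to be too high in PLAN relative to control. The expected ratio with equal harm is about 1.5 to 2.0 with evenly spread onset, and 1.9 to 3.0 if onset precedes the first session, for d from 0.5 down to 0.2. A reader might take the upper range as the size of the bias; it needs every episode to begin before coaching starts.

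All these ratios rest on an assumed d and on independent contacts. If some patients never disclose distress, the ratio is smaller. If social workers detect more per contact than interviewers do, it is larger. The consequence is for the interpretation of end-of-study AE reporting and of the pilot's safety signal; the feasibility, acceptability and efficacy analyses are untouched. For a 50-patient pilot this is a cheap improvement worth making before data collection.

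**What to change.** 1. Add one short AE question set (distress, family conflict, hospital or emergency visit) to the existing post-intervention interview, worded identically in both arms.
2. Use the same look-back window in both arms, counted from baseline, because PLAN's assessment can fall up to about two weeks later than the control's.
3. Name the chart and EHR review already done in both arms as an AE source, over a common window.
4. Base any by-arm AE table on these two sources, and list events noted in coaching sessions separately.
5. Report the baseline-adjusted difference in post-intervention FACT-G with its confidence interval as descriptive support. It should not be offered as proof of no harm: FACT-G is a quality-of-life scale, and 25 per arm gives 80% power, unadjusted, only for a standardized difference of about (1.96 + 0.84) × √(2/25) = 0.8.

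The cost is a few interview questions, one extra table and one descriptive model. Expedited reporting is unchanged. Recall in PLAN may be somewhat older where the interview falls later, so the comparison would be fairer but not perfect.
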